6.2.2 Dosage Adjustments, Delays, Rules for Withholding or Restarting, Permanent Discontinuation

6.2.2.1 Amgen Investigational Product: AMG 330

Subjects will be monitored continuously for adverse events while on study therapy.

Subjects will be instructed to notify their physician immediately for any and all adverse events. The criteria presented in this section for dose modifications and delays for AMG 330 are meant as general guidelines.

Criteria for Dose Delay or Dose Reduction

Subjects will receive continuous AMG 330 therapy as long as they have not had disease progression or an adverse event requiring dose modification, as described below.

Subjects who experience a grade 4 non-hematologic adverse event will not receive additional protocol-related therapy and will be removed from study unless discussed and agreed upon by the Sponsor and investigators that it is in the best interest of the subject to receive additional therapy with AMG 330 (eg, if the subject has demonstrated a response to therapy).

Dose modifications, interruptions, or delays may occur in the setting of lower grade adverse events based on the clinical judgement of the investigator, and in consultation

with the sponsor. Dose reductions should be to the previous lower dose level, or to a dose level in between the previous dose level and the current dose level, after discussion between the investigator and the sponsor.

No more than 2 dose level reductions of AMG 330 will be allowed per subject. If a third dose reduction is required, the subject must discontinue AMG 330 (and pembrolizumab, if receiving combination therapy based on response to therapy). Dose re-escalation after a dose reduction may occur in limited circumstances (such as a change in attribution of adverse event, or if re-escalation is in the best interest of the subject) after discussion and agreement between the sponsor and the investigator.

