For an adverse event requiring dose modification, AMG 330 (and pembrolizumab for subjects receiving combination therapy) should be interrupted to allow recovery from the adverse event. Re-initiation of study drug cannot occur until adverse event decreases to grade ≤ 1 . In case of delayed recovery to grade ≤ 1 from treatment-related adverse events that results in a delay of treatment for > 21 days, the subject will not receive additional protocol-related therapy and will be removed from study unless discussed and agreed upon by the sponsor and investigators that it is in the best interest of the subject to receive additional therapy with AMG 330 and pembrolizumab (eg, if subject demonstrated response to therapy).

Assessment of causality (chronology, confounding factors such as disease, concomitant medications, diagnostic tests and previous experience with the agent) must be determined and documented by the investigator, prior to dose modification.

In case of grade 2 CRS, administration of AMG 330 can be continued on the currently tested dose level for 8 hours, and treatment provided to mitigate CRS symptoms. If symptoms do not improve to grade 1, the dose will be de-escalated by 50% for an additional 24 hours. If CRS grade 2 resolves to grade 1, the dose can be re-escalated back to the level being tested. If symptoms persist, AMG 330 infusion will be interrupted and pembrolizumab infusion will be delayed until symptoms improve to grade 1. If treatment is interrupted for < 24 hours, the interrupted AMG 330 dose can be resumed and re-escalated back to the tested dose level. If treatment is interrupted for > 24 hours, restart or repeat rules apply (see below).

In case of grade 3 CRS, AMG 330 treatment must be interrupted and pembrolizumab treatment postponed. Sponsor has to be consulted prior to a planned re-start. In case

of grade 4 CRS, treatment must be permanently discontinued. See [Section 6.8](#) for specific instructions for the management of CRS.

If the same grade 3 non-hematologic adverse event recurs despite a dose reduction, a second dose reduction versus discontinuation of the subject from further protocol therapy should be discussed and agreed upon the sponsor and investigators.

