7.1 Discontinuation of Study Treatment

Subjects (or a legally authorized representative) can decline to continue receiving investigational product and/or other protocol-required therapies or procedures at any time during the study but continue participation in the study. If this occurs, the investigator is to discuss with the subject the appropriate processes for discontinuation from investigational product or other protocol-required therapies and must discuss with the subject the possibilities for continuation of the Schedule of Activities (see [Table 1-1](#), [Table 1-3](#), [Table 1-5](#)) including different options of follow-up (eg, in person, by phone/mail, through family/friends, in correspondence/communication with other treating physicians, from the review of medical records) and collection of data, including endpoints, adverse events, and device-related events and must document this decision in the subject's medical records. Subjects who have discontinued investigational product and/or other protocol-required therapies or procedures should not be automatically removed from the study. Whenever safe and feasible, it is imperative that subjects remain on-study to ensure safety surveillance and/or collection of outcome data.

Subjects may be eligible for continued treatment with Amgen investigational product(s) and/or other protocol-required therapies by a separate protocol or as provided for by the local country's regulatory mechanism, based on parameters consistent with [Section 11.3](#).

Reasons for early removal from protocol-required investigational product(s) or procedural assessments may include any of the following:

- Decision by Sponsor
- Lost to follow-up
- Death
- Adverse event
- Subject request
- Decision by investigator
- Ineligibility determined
- Protocol deviation

- Non-compliance
- Disease progression
- Requirement for alternative therapy
- Protocol-specified criteria
- Pregnancy
- Recurrent grade 2 pneumonitis
- Completion of 35 treatments (approximately 2 years) with pembrolizumab

Note: The number of treatments is calculated starting with the first dose of pembrolizumab.

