7.2.1 Reasons for Removal From Study

Reasons for removal of a subject from the study are:

- Decision by sponsor
- Withdrawal of consent from study
- Death
- Lost to follow-up

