# 5.4 Endpoints

### Treatment-emergent Adverse Event (TEAE)

Treatment emergent adverse event refers to an adverse event that starts on or after first dose of any IP (as indicated by the flag whether an event starts before first dose of any IP is "No" or missing on the Events CRF page) and up to and including end of study date. This reporting window also applies to treatment-emergent serious adverse events (SAEs).

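### Protocol 6.2.2.1 makes removal from the study the default after severe toxicity, in conflict with 7.1 and 7.2.1, and a literal reading puts those subjects' safety follow-up at risk

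*Protocol*

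**What the plan says.** Two sentences in Protocol 6.2.2.1, under the criteria for dose delay or dose reduction, tie the end of treatment to the end of participation.

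- After a grade 4 non-hematologic adverse event, such a subject "will not receive additional protocol-related therapy and will be removed from study unless discussed and agreed upon by the Sponsor and investigators". The agreement must be that additional AMG 330 is in the subject's interest.
- For a treatment delay of more than 21 days caused by slow recovery from a treatment-related event: "the subject will not receive additional protocol-related therapy and will be removed from study unless discussed and agreed upon by the sponsor and investigators". Here the agreement must be to give further AMG 330 and pembrolizumab.

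The section opens with a qualifier: "The criteria presented in this section for dose modifications and delays for AMG 330 are meant as general guidelines".

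Section 7.1 takes a different line. "Subjects who have discontinued investigational product and/or other protocol-required therapies or procedures should not be automatically removed from the study", and, where safe and feasible, "it is imperative that subjects remain on-study to ensure safety surveillance and/or collection of outcome data". Section 7.2.1 begins "Reasons for removal of a subject from the study are" and lists four: sponsor decision, withdrawal of consent, death and loss to follow-up. Adverse event is listed in 7.1, but only as a reason for stopping product or procedural assessments.

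**The concern.** The primary objective is safety. Under the two sentences in 6.2.2.1, whether a subject stays under observation depends on having had severe or slowly resolving toxicity. The only stated way to stay on study is an agreement to give more drug. Neither sentence describes a subject who is off treatment but still followed.

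If sites act on that wording, the missing safety data would not be missing at random. They would come from the subjects with the worst toxicity, so later adverse events and serious adverse events could be undercounted. Two sites reading different sections could also handle the same subject differently.

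**Working it through.** The point rests on no sample size, rate or error level, so there is no plan figure to reproduce. The check sets the texts side by side.

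**1. Is there a conflict?** Yes.
- 6.2.2.1 makes removal automatic unless further therapy is agreed. 7.1 says removal should not be automatic after treatment stops.
- 6.2.2.1 removes for toxicity. 7.2.1 does not list toxicity. A sponsor decision is listed there, but in 6.2.2.1 the sponsor's agreement is needed to avoid removal, not to bring it about.
- 6.2.2.1 is also uneven within itself. Its dose-delay note and its permanent-discontinuation list attach only the end of treatment to an event or interruption lasting more than 21 days.

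**2. What follow-up does the protocol still require?**
- 6.2.2.1, end of the permanent-discontinuation text: after any premature discontinuation, sites should make every effort to complete the end-of-treatment and safety follow-up examinations before discharging the subject.
- 8.1.3: two safety visits, 30 (+7) days after the last dose of each drug, whatever the reason for stopping.
- 8.2.5.1.1: adverse events through the safety visit or 30 days after treatment ends, whichever is later.
- 8.2.5.1.2: serious adverse events through the safety visit or 90 days (30 with new anticancer therapy), whichever is later.
- 8.2.5.3: reported events are followed to resolution or stabilization.
- 8.2.4.3: vital status for all subjects, including those who stopped visits.

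**3. What is exposed under a literal reading?**
- If participation ends at the removal decision, the upper bound per subject is the 30-day adverse event period and the 90-day serious adverse event period (30 with new anticancer therapy).
- If removal waits for a visit 30 days after the last dose, and cessation is taken as that last dose, 90 − 30 = 60 days of serious event collection remain after it. 8.2.5.1.3 states no monitoring duty after the end of study, which leaves those days unclear for a removed subject.
- Later response assessments stop. SAP 5.4 censors duration of response at the last adequate assessment, so censoring would then be linked to toxicity.

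**4. What is not exposed?**
- A subject who has had a DLT is DLT evaluable under 6.2.1 whatever follows, so a DLT already observed still counts.
- Deaths are largely protected by the vital status requirement.

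**5. Does the SAP window depend on removal?** Unclear. SAP 5.4 counts treatment-emergent events "up to and including end of study date". SAP 5.3 defines that date at study level, as the last subject's last visit. On that definition a subject's removal does not close the window, although uncollected events would still be absent from it.

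**The case against.** The strongest reply is that 6.2.2.1 does not say when removal happens. The same section asks for the follow-up examinations before discharge, and 8.1.3 applies to any reason for discontinuation. A site reading the section as a whole would complete those visits first. The adverse event periods also run from the end of treatment, not from study status. This part stands. A reader might infer that safety follow-up is lost for these subjects, but the documents do not say so.

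A reader might also infer that Section 7 forbids removal. It does not. Its wording is advisory and limited to what is safe and feasible, and 7.2.1 allows removal by sponsor decision.

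Nor can every late event be charged to this clause. 6.2.2.2.2 says immune-related events may appear several months after the last pembrolizumab dose. Some of these would fall outside the collection periods for every subject, and 8.1.4 plans no long-term follow-up for anyone.

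The guideline qualifier helps less. It describes criteria for dose modifications and delays, while the removal sentences concern participation and are worded as a requirement. The follow-up provisions show the intent, but they do not cancel those sentences.

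**Conclusion.** The contradiction is real and should be corrected. Its consequence is a risk that depends on a site reading the removal wording literally. In that case follow-up could be cut short selectively in subjects with severe toxicity, within the per-subject upper bounds given above.

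The number of subjects cannot be stated. It is tempting to borrow the phase 1a figures in Protocol 4.3: 6 of 49 (12.2%) stopped AMG 330 for adverse events, and 40 (81.6%) had events of grade 3 or higher. Neither measures these triggers. The first covers discontinuation for adverse events without regard to grade, and the second does not separate grade 4 or non-hematologic events. Neither describes delays over 21 days, and neither says how often follow-up would actually be missed. With about 20 subjects planned, even one shortened follow-up would affect the safety summary, but that is no estimate of how often it would happen.

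**What to change.** Reconcile the two sentences in 6.2.2.1 with the follow-up text later in that section and with 7.1, 7.2.1 and 8.1.3, so that stopping treatment and leaving the study are stated separately. For example, replace the removal phrase in each with wording that these subjects stay on study, whenever safe and feasible, for the safety follow-up visits in 8.1.3 and the collection periods in 8.2.5.1, and that removal from the study occurs only under 7.2.1. Leave the treatment rule and its sponsor and investigator exception as they are.

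The cost is two sentences in a protocol amendment. The visits and collection periods already exist.

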- Isolated grade 3 elevation of amylase or lipase not associated with clinical or radiological evidence of pancreatitis
- Grade 3 endocrinopathy that is well controlled by hormone replacement
- CRS meeting any of the criteria listed below:
 - Grade 2 CRS that does not resolve, with or without intervention to grade 1 within 7 days will be considered a DLT
 - Grade 3 CRS that does not resolve, with or without intervention to ≤ grade 2 within 5 days, will be considered a DLT
 - Any grade 4 CRS
- Any grade 5 toxicity
- Receive less than 70% of the planned cumulative dose of AMG 330 or miss more than 1 dose of pembrolizumab during the first cycle due to investigational product(s) related toxicity that does not meet the DLT criteria listed above

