Please also refer to specific guidance on restart after CRS in [Section 6.8](#). Restarting the infusion after a treatment interruption requires care. The re-start should be performed in the hospital, under supervision of the investigator or designee, if the reason for the interruption was other than a technical issue or the interruption exceeded 4 hours independent of reason. Assessments should be performed after infusion re-start depending on the length of the interruption. The subject should be hospitalized for at least 48 hours after re-start of the infusion.

In case of an AMG 330 infusion interruption of > 24 hours, regardless of the reason for interruption, re-start of the infusion (repeat cycle) should be performed using step doses, which will be defined upon consultation with the sponsor. Only 2 repeat cycles may be performed in cycle 1. For cycle 2 and beyond, additional repeat cycles can be permitted upon discussion and agreement between the investigator and sponsor.

Step doses will be performed within 1 – 2 weeks (\pm 1 day) to return to the interrupted AMG 330 dose level, and the number and duration of repeat step doses will depend on the level of interrupted AMG 330 dose. During this 1-2 weeks, [Table 1-7 Schedule of Activities](#) should be followed (eg, for AMG 330 doses interrupted at [REDACTED] μ g/day and below, 2 step doses can be used: [REDACTED] μ g/day for 3 days followed by [REDACTED] μ g/day for 4 days; for doses interrupted above [REDACTED] μ g/day, 3 step doses can be used: [REDACTED] μ g/day for 1 day followed by [REDACTED] μ g/day for 3 days followed by [REDACTED] μ g/day for 3 days). In case of AMG 330 infusion interruption for < 24 hours, regardless of the reason for interruption, restart of infusion should be performed at the same dose level as the last dose level. Administration of pembrolizumab will remain on the Q3W schedule.

After 2 unsuccessful restarts, the subject may remain on the study and continue AMG 330 treatment with a previously tested target dose that has been well tolerated. The dose of pembrolizumab will remain unchanged.

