6.2.2.2 Non-Amgen Investigational Product(s): Pembrolizumab

6.2.2.2.1 Dose Modification of Pembrolizumab if AMG 330 has been Interrupted

If toxicities due to AMG 330 do not resolve to grade ≤ 1 within 7 days of treatment interruption and supportive care as outlined, pembrolizumab may be postponed until both may be resumed per protocol. If AMG 330 is discontinued, pembrolizumab treatment may be continued following discussion and agreement between the investigator and Sponsor.

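### For non-CRS, non-DLT toxicity attributed to AMG 330, protocol Sections 6.2.2.1 and 6.2.2.2.1 disagree on a pembrolizumab dose that falls due during the interruption

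*Protocol*

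**What the plan says.** Four places in the protocol bear on a pembrolizumab dose that falls due while AMG 330 is interrupted for toxicity.

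- **Section 6.2.2.1, Criteria for Dose Delay or Dose Reduction.** For an event requiring dose modification, "AMG 330 (and pembrolizumab for subjects receiving combination therapy) should be interrupted to allow recovery from the adverse event". It continues: "Re-initiation of study drug cannot occur until adverse event decreases to grade ≤ 1". There is no waiting period.
- **Section 6.2.2.2.1**, on pembrolizumab when AMG 330 has been interrupted. The trigger is "If toxicities due to AMG 330 do not resolve to grade ≤ 1 within 7 days of treatment interruption and supportive care as outlined". The action is "pembrolizumab may be postponed until both may be resumed per protocol".
- **Section 4.1.1 (repeated in SAP Section 3.1.1).** In cohort 1 the day 36 and day 57 pembrolizumab doses are to be given if no DLT has occurred at the current AMG 330 dose level. No other condition on toxicity is stated there.
- **Section 6.2.2.1, Restarting the Infusion.** After the text on restarts following interruptions of more and of less than 24 hours, it says: "Administration of pembrolizumab will remain on the Q3W schedule".

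Section 6.2.1 then counts missed doses. It is a DLT to "miss more than 1 dose of pembrolizumab during the first cycle due to investigational product(s) related toxicity" where the toxicity meets no other DLT criterion. One of the three routes to DLT evaluability also requires no more than 1 missed pembrolizumab dose. The SAP (Sections 5.4 and 6.2) refers back to protocol Section 6.2.1 for both. Neither document says whether a postponed dose is a missed dose.

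**The concern.** The first two rules address the same event and give different answers. One holds pembrolizumab from the moment AMG 330 is interrupted. The other provides no ground for holding it in the first week and leaves the matter optional after that. A site reading Section 6.2.2.1 would withhold a scheduled dose of a checkpoint inhibitor during unresolved toxicity. A site reading Section 6.2.2.2.1, or in cohort 1 the dosing description in Section 4.1.1, could give it.

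What is at stake is mainly consistent treatment of subjects with active toxicity in a combination for which the protocol reports no combination toxicology studies (Section 2.2.2.3). A secondary matter is that held doses enter the DLT definition and the evaluability rule, so handling that differs between sites could reach the primary endpoint.

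**Working it through.** There is no stated figure to reproduce. The check is a comparison of the rules, an example, and two short counts.

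**1. Which toxicities are left in conflict.** Events with their own instruction are set aside:

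- CRS: Section 6.2.2.1 and Table 6-5 give pembrolizumab instructions by grade.
- DLTs: Section 6.2.1 stops dosing for the individual, and Section 4.1.1 makes the cohort 1 doses conditional on no DLT.
- Immune-related events and infusion reactions attributed to pembrolizumab: Tables 6-3 and 6-4.
- Hepatotoxicity: Table 11-2.

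What remains is toxicity attributed to AMG 330 that interrupts the infusion, is neither CRS nor a DLT, and is outside those tables.

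**2. The rules side by side for that remainder.**

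| Time since interruption, toxicity above grade 1 | Section 6.2.2.1 | Section 6.2.2.2.1 |
|---|---|---|
| First 7 days | Hold | No provision to postpone |
| After 7 days | Hold | Postponement optional |

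**3. An example.** Section 6.2.1 exempts grade 3 rash from the DLT definition. Rash of any grade was reported as related to AMG 330 in 30.6% of monotherapy subjects (Section 4.3), so the event type is not far-fetched. Suppose a cohort 1 subject has grade 3 rash attributed to AMG 330 on day 33, AMG 330 is interrupted, and pembrolizumab is due on day 36.

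- Section 6.2.2.1: hold until grade 1 or lower.
- Section 6.2.2.2.1: the 7-day condition cannot be met before day 33 + 7 = 40.
- Section 4.1.1: no DLT on days 29 to 35, so the dose is given.
- The 3-day window in Table 6-2 extends the dose to day 36 + 3 = 39, still short of day 40.

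**4. How often a due date falls in the disputed week.** Assume that interruptions last at least 7 days and that start days are uniform over the 21-day interval.

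- Ignoring the dosing window: 7/21 = 0.33.
- If doses due in the last 3 of the 7 days are moved past day 7 under the Table 6-2 window, which applies from the second pembrolizumab dose: (7 − 3)/21 = 4/21 = 0.19.

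The documents do not give the frequency of such interruptions, so these are conditional shares and not rates per subject.

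**5. Reach into the DLT endpoint.**

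- Doses planned during the cycle 1 infusion: days 15, 36 and 57 (cohort 1) or days 1, 22 and 43 (cohort 2), so 3 in each.
- The DLT criterion needs more than 1 missed, so at least 2 of 3.
- Doses are 21 days apart and 7 < 21, so the disputed week contains at most 1 due date per episode.
- Two such missed doses therefore need two episodes in cycle 1. That is possible, since Section 6.2.2.1 allows two repeat cycles in cycle 1, but it is not the usual course.
- The evaluability criteria are alternatives. A subject with no DLT who completes the period is evaluable whatever the number of missed doses.

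**The case against.** The strongest reply is that the two sections can be read together. Section 6.2.2.2.1 is permissive: it says when pembrolizumab may be postponed and does not forbid an earlier hold under Section 6.2.2.1. Section 6.2.2.1 also describes its criteria as general guidance. Most serious events are handled elsewhere, and the consequence for the DLT endpoint is small.

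The last two arguments stand, and they set the limits of this point. The first two do not remove the conflict. The guidance statement is about AMG 330 modifications, while the bar on re-initiation is worded as a prohibition. A section written specifically for pembrolizumab during an AMG 330 interruption would have no use for a 7-day trigger if the drug were already on hold from day 0. Nothing states which section prevails.

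Three stronger readings are tempting but not supported:

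- **That the Q3W sentence is a third rule ordering dosing during active toxicity.** It sits in the restart instructions of Section 6.2.2.1. Restart after toxicity there generally presupposes grade 1 or lower, with one exception by agreement for dose reduction when the event is not clinically relevant. The sentence directly before it begins: "In case of AMG 330 infusion interruption for < 24 hours, regardless of the reason for interruption, restart of infusion should be performed". Whether it covers only those short interruptions or also repeat cycles is unclear. That is an ambiguity of scope and not a separate conflicting rule.
- **That every toxicity other than CRS is affected.** Step 1 of the working shows otherwise.
- **That the same clinical course will readily be a DLT at one site and not at another.** It takes two missed doses. In addition, Section 6.2.2.1 treats a cycle interrupted for more than 24 hours but less than 21 days as not evaluable for DLT unless the cause was a DLT, and that statement does not depend on pembrolizumab.

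**Conclusion.** The protocol contradicts itself on one defined question: whether a pembrolizumab dose that falls due during an AMG 330 interruption is held, when the toxicity is attributed to AMG 330, is neither CRS nor a DLT, and lies outside Tables 6-3, 6-4 and 11-2. Section 6.2.2.1 holds it at once. Section 6.2.2.2.1 allows postponement only after 7 unresolved days, as an option. In cohort 1, Section 4.1.1 gives the day 36 and day 57 doses unless a DLT has occurred.

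The conclusion rests on the text alone. The 33% and 19% shares are illustrations that depend on uniform start days and on interruptions of at least a week. The effect on the primary endpoint is limited, to at most one disputed-week dose per episode, but it is not defined, because the status of a postponed dose is not stated. The passages need reconciling because they decide whether a checkpoint inhibitor is given during unresolved toxicity. No view is taken here on which rule is right.

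**What to change.** 1. Reconcile Section 6.2.2.1 (Criteria for Dose Delay or Dose Reduction) with Section 6.2.2.2.1, and with the cohort 1 dosing text in Section 4.1.1, into one statement of what happens to a scheduled pembrolizumab dose while AMG 330 is interrupted for toxicity. Place it in Section 6.2.2.2.1 and cross-refer to it from Section 6.2.2.1. Align the repeated text in SAP Section 3.1.1.
2. State which interruptions the Q3W sentence under Restarting the Infusion applies to.
3. State in Section 6.2.1 whether a postponed pembrolizumab dose counts as missed for the DLT criterion and for evaluability. The SAP inherits this by reference.

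The clinical content of the rule is for the sponsor to decide. The cost is a wording change, with no added visits, tests or subjects.
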